- QTcF interval ≥ 501 msec and > 60 msec prolongation from baseline (defined as the average QTcF value from pre-dose C1D1 ECGs), or associated with Torsades de pointes, polymorphic ventricular tachycardia, or serious arrhythmia
- Prolonged delay (> 2 weeks) in initiating Cycle 2 due to treatment-related toxicity;
- Any treatment-related toxicity that causes the subject to discontinue treatment during Cycle 1
- Any Grade 5 toxicity.

Duration of Treatment

Subjects may continue to receive study therapy until the earliest of the following: subject withdrawal from study, confirmed progression of cancer, intolerable study-drug-related toxicity despite appropriate dose modification, the development of intercurrent illness that precludes continued study therapy, pregnancy or breastfeeding, substantial noncompliance with study procedures, completion of Treatment Phase comprising up to 35 treatment cycles for FLX475, or study discontinuation by Sponsor.

Study Endpoints:

Efficacy:

The primary efficacy endpoint of the study is objective response rate (ORR), defined as the proportion of subjects who have best overall response of CR or PR as determined using RECIST 1.1 ([Appendix 4](#)) for subjects with melanoma.

Other efficacy endpoints are as follows:

- Overall Survival (OS), defined as the time from the date of start of treatment to the date of death from any cause. Subjects who are lost to follow-up and those who are alive at the date of data cutoff will be censored at the date the subject was last known alive, or date of data cutoff, whichever occurs first.
- Clinical Benefit Rate (CBR), defined as the proportion of subjects who achieve a CR, a PR, or durable SD duration of at least 6 months from start of study treatment.
- Time to Response, defined as the interval from start of study treatment to the first documentation of CR or PR.
- Duration of Response, defined as the interval from the first documentation of CR or PR to the earlier of the first documentation of PD or death from any cause.
- Progression-free Survival (PFS), defined as the interval from the start of study treatment to the earlier of the first documentation of PD or death from any cause.

Safety:

The primary safety endpoint in the safety run-in portion of the study is safety and tolerability by the determination of AEs, including DLTs. The following safety parameters will be characterized and summarized:

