- Treatment-emergent adverse events (TEAEs) and SAEs together with all other safety parameters
- Number (%) of subjects who discontinue treatment due to TEAEs
- Time to treatment failure due to toxicity, defined as the time from the date of start of treatment to the date that a subject discontinues study treatment due to TEAEs
- Dose-limiting toxicity (defined in [Section 10.4](#))
- Laboratory abnormalities
- Vital sign abnormalities
- Adverse ECG findings

Pharmacokinetics:

Plasma concentrations of FLX475 will be determined with a validated bioanalytical method, and listed and summarized by time point. No PK parameters (e.g. C_{max} and AUC) will be calculated.

Pharmacodynamics:

Changes in immune parameters, e.g., lymphocyte subpopulations and plasma cytokines or chemokines in peripheral blood or in tumor

Statistical Methods:

Analysis Sets

The following sets of data will be defined for this study:

Full Analysis Set (FAS): All subjects enrolled in the study. The FAS will be used to summarize subject disposition, demographics and baseline data, cancer history, and exposure to study treatment.

Safety Analysis Set: All subjects who receive at least one dose of the investigational product, FLX475 (even a partial dose). This set will be used for the analysis of all safety data, including adverse events, vital signs, and clinical laboratory data.

Efficacy Eligible Set: All subjects who receive at least one dose of FLX475 in combination with ipilimumab, have measurable disease at baseline per RECIST v1.1, and have at least one post-baseline scan or discontinue study treatment as a result of progressive disease, death, or a treatment-related adverse event before the first post-baseline scan. This set will be used for sensitivity analysis of the primary efficacy endpoint, ORR.

Efficacy Evaluable Set: All subjects who complete at least one cycle of FLX475 in combination with ipilimumab and have a baseline and at least one post baseline on-study assessment of tumor response. This set will serve as the primary basis for analysis of all efficacy endpoints, including ORR, DOR, PFS, and OS.

As warranted by the data, efficacy may also be assessed in a Per-Protocol Population comprising all Efficacy Evaluable subjects who have no major protocol violations, as defined by the Sponsor prior to database lock.

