12.1.2.3 Analysis Sets

The allocation of subjects to analysis sets will be determined prior to database lock. For the purpose of analysis, the following populations will be defined:

Full Analysis Set: All subjects enrolled in the study, also known as the “Intent-to-Treat” (ITT) population.

Safety Analysis Set: All subjects who receive at least one dose of the investigational product, FLX475 (even a partial dose).

Efficacy Eligible Set: All subjects who receive at least one dose of FLX475 in combination with ipilimumab, have measurable disease at baseline per RECIST v1.1, and have at least

one post-baseline scan or discontinue study treatment as a result of progressive disease, death, or a treatment-related adverse event before the first post-baseline scan.

Efficacy Evaluable Set: All subjects who complete at least one cycle of FLX475 and ipilimumab and have a baseline and at least one post baseline on-study assessment of tumor response.

As warranted by the data, efficacy may also be assessed in a Per-Protocol Population comprising all Efficacy Evaluable subjects who have no major protocol violations, as defined by the Sponsor prior to database lock.

Pharmacokinetic (PK) Analysis Set: All subjects who receive at least 1 dose of FLX475 in combination with ipilimumab and have measurable plasma concentrations of FLX475.

Pharmacodynamic (PD) Analysis Set: All subjects who receive at least 1 dose of investigational product and have sufficient PD data to derive at least 1 PD measurement.

12.1.3 *Subject Disposition*

The number and percentage of subjects who are enrolled, treated, complete the study, and discontinue from the study will be presented for the Full Analysis Set. A summary of reasons for discontinuation will be provided. The number of subjects included in the Safety Analysis and Efficacy Evaluable Sets will be summarized and the reasons for excluding subjects from the Efficacy Analysis Set will be listed.

12.1.4 *Demographic and Other Baseline Characteristics*

Descriptive statistics will be used to summarize demographic and baseline characteristics of subjects in each analysis set. Subject characteristics to be tabulated include: age, sex, race, ethnicity, baseline performance status, primary diagnosis, disease stage at diagnosis and baseline, prior therapies (including systemic therapies, radiation, and surgeries), and best response to prior cancer therapies.

12.1.5 *Prior and Concomitant Therapy*

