All investigator terms for medications recorded in the eCRF will be coded to an 11-digit code using the World Health Organization Drug Dictionary (WHO DD) drug codes. The number (percentage) of subjects who took prior and concomitant medications will be summarized for the FAS by treatment, Anatomical Therapeutic Chemical class, and WHO DD preferred term. Prior medications will be defined as medications that were stopped before the first dose of study treatment. Concomitant medications will be defined as medications that (1) started before the first dose of study treatment and were continuing at the time of the first dose of study treatment, or (2) started on or after the date of the first dose of study treatment up to 30 days after the subject's final dose. All medications will be presented in subject data listings.

12.1.6 *Efficacy Analyses*

The primary efficacy endpoint is ORR, and the secondary efficacy endpoints include PFS, TTR, DOR and OS. Tumor-related endpoints will be analyzed for the FAS and Efficacy Evaluable Sets, as appropriate. An additional sensitivity analysis of ORR will be performed for the Efficacy Eligible Set. Efficacy will also be explored in subgroups of special interest, notably subjects who are anti-PD-(L)1 refractory (as defined in [Appendix 8](#)) and other prognostic subgroups pre-specified in the SAP.

ORR will be defined as the proportion of subjects who are responders, i.e., CR and PR; the exact 95% confidence interval for ORR will be calculated using the Clopper-Pearson method. The CBR (CR + PR + SD) will also be calculated; SD in the CBR determination is defined as SD that persists for ≥ 6 months. The ORR and CBR analysis will be based on RECIST v1.1.

Time-to-event endpoints, including PFS and OS, will be summarized descriptively and graphically using Kaplan-Meier (KM) methodology. KM estimates for the median, first, and third quartiles will be determined along with 95% confidence intervals (CIs). The Brookmeyer-Crowley method will be used for the CI calculations. For the subset of subjects who have a CR or PR, DOR will be summarized similarly using the Kaplan-Meier method. TTR will be defined from the start of treatment to the first documented CR or PR and will be summarized descriptively as a continuous variable.

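### The set named as primary for all efficacy endpoints requires surviving a cycle and being assessed; OS has no alternative set, and the alternatives for ORR and PFS are not ranked

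*Protocol*

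**What the plan says.** The synopsis (Analysis Sets) says of the Efficacy Evaluable Set: "This set will serve as the primary basis for analysis of all efficacy endpoints, including ORR, DOR, PFS, and OS". Section 12.1.2.3 gives the membership rule without the primary label: "All subjects who complete at least one cycle of FLX475 and ipilimumab and have a baseline and at least one post baseline on-study assessment" (the assessment meant is one of response in the tumor). Neither place makes an exception for early progression, death or toxicity.

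The Efficacy Eligible Set needs no completed cycle. Besides scanned subjects, it keeps those who "discontinue study treatment as a result of progressive disease, death, or a treatment-related adverse event before the first post-baseline scan". Its use is confined to one endpoint. The synopsis says "This set will be used for sensitivity analysis of the primary efficacy endpoint, ORR", and Section 12.1.6 says "An additional sensitivity analysis of ORR will be performed for the Efficacy Eligible Set".

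The two places differ on the Full Analysis Set (FAS). The synopsis lists only non-efficacy uses: "The FAS will be used to summarize subject disposition, demographics and baseline data, cancer history, and exposure to study treatment". Section 12.1.6 says: "Tumor-related endpoints will be analyzed for the FAS and Efficacy Evaluable Sets, as appropriate".

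OS is "defined as the time from the date of start of treatment to the date of death from any cause". The first on-treatment scan is due at 9 weeks, with a window of 7 days either side (Section 11.3.1.1).

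The sample-size rationale (synopsis and Section 12.1.1) lists early progression and early death among the evaluability categories, but first requires Efficacy Evaluable membership.

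The SAP does not summarize efficacy, because the study stopped early (SAP 6.4.1.1, 7.4.1, 7.7). It defines only the FAS and the Safety Analysis Set (SAP 7.2).

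**The concern.** Membership of the lead set is settled by what happens after treatment starts. The OS clock begins at first dose, but a subject enters the set only by completing a cycle and being assessed. Anyone who dies before that is removed instead of counted as a death, so the survival curve starts with a stretch in which no member can die. PFS loses deaths before the first assessment in the same way. ORR loses early failures that belong in its denominator.

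The protocol itself produces such exits. A subject with a DLT in Cycle 1 should normally stop treatment (Section 10.5.1), and no scan is scheduled before week 9.

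The trial has one arm, so no control group shares the selection. The estimates are read directly against an outside ORR of about 14% (Section 6.3) or 10–15% (Section 12.1.1).

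**Working it through.** **Stated figure.** The sample size of 20 rests on clinical grounds, with no alpha, power or decision rule, so there is no calculation to reproduce. The check covers who is in each set and how far estimates could move.

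**Who is in each set** (subjects dosed with both drugs, with measurable disease at baseline):

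| Subject | Efficacy Evaluable | Efficacy Eligible | FAS |
|---|---|---|---|
| Stops in Cycle 1 for PD, death or related AE; never assessed | out | in | in |
| Stops in Cycle 1 for another reason, e.g. withdrawal; never assessed | out | out | in |
| Stops in Cycle 1, scanned afterwards | out | in | in |
| Completes Cycle 1, stops because of death before any assessment | out | in | in |
| Completes Cycle 1, scanned early or at discontinuation | in | in | in |

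**Which endpoints each set covers.** Efficacy Evaluable: ORR, DOR, PFS and OS. Efficacy Eligible: ORR only. FAS: tumor-related endpoints under 12.1.6, which means ORR and plausibly PFS. OS is therefore tied to the first column alone.

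**ORR.** Numbers of responders and losses are assumptions; the documents give none. Exact (Clopper-Pearson) 95% intervals, as the protocol specifies:
- All 20 treated: 4/20 = 20.0% (5.7 to 43.7), width 43.7 − 5.7 = 38.0 points.
- Two non-responders excluded: 4/18 = 22.2% (6.4 to 47.6).
- Four non-responders excluded: 4/16 = 25.0% (7.3 to 52.4).
- Same four, of whom three meet the Efficacy Eligible rule: 4/19 = 21.1% (6.1 to 45.6). The sensitivity analysis recovers 25.0 − 21.1 = 3.9 of the 5.0 points.

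If a fraction u is excluded and all of them are non-responders, an ORR p reads as p/(1 − u). For p = 14%, that gives 14.7%, 15.6% and 17.5% at u = 5%, 10% and 20%.

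Section 6.3 treats an ORR above 20–30% as preliminary support. With a true ORR of 14% in 20 subjects, exceeding 20% needs at least 5 responders, which has probability 13.7%. With one to five non-responders excluded, 4 responders are enough, and the probability is 30.4%.

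**OS.** Assume exponential survival with median m of 8 to 12 months. Deaths before day d are a fraction 1 − exp(−ln2 × d/(30.4375 m)). Given survival to day d, the median from start of treatment is m + d/30.4375.

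| Deaths excluded before | Fraction removed (m = 12 to 8) | Rise in median |
|---|---|---|
| Day 21 (end of Cycle 1) | 3.9% to 5.8% | 0.7 months |
| Day 63 (week 9) | 11.3% to 16.4% | 2.1 months |
| Day 70 (end of scan window) | 12.4% to 18.1% | 2.3 months |

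If the hazard up to day 63 is half the later hazard, with the overall median unchanged, the day-21 row becomes 2.2% to 3.4% and 0.3 months. The day-63 row becomes 6.3% to 9.8% and 1.0 months.

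**Evaluability rule.** Someone who dies of melanoma before week 9 is listed as an early death and so as evaluable. If that person had not completed a cycle, or had no tumor assessment of any kind, the Efficacy Evaluable precondition fails and the listing has no effect. The same holds for early progression.

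**The case against.** The strongest reply is that the rule has no operative effect. The SAP declares that efficacy will not be summarized. The expansion decision that used the evaluable count is moot after the early stop, and it needed a protocol amendment anyway. This stands, and it limits the severity. It does not make the rule sound: the SAP supplies no replacement efficacy set, so the synopsis would still govern any ORR or OS that is quoted.

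Second, much of the remedy is already planned. The FAS is all enrolled subjects, and enrollment is dated at start of treatment (Section 11.1), so it is close to all treated. Section 12.1.6 uses it for tumor-related endpoints. This stands for ORR and, on a natural reading, for PFS. What remains there is the ranking and the conflict with the synopsis. For OS, calling survival a tumor-related endpoint is strained.

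Third, a reader might infer that the lead ORR must be too high, by 1/(1 − u). The documents do not support that. Imaging continues after treatment stops without PD (Sections 8.2.3 and 9.1.4), so a subject who stops in Cycle 1 for toxicity can respond later and is still excluded. With one such responder, 5/20 = 25.0% would read 4/19 = 21.1%, a downward shift.

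Fourth, a reader might infer that no unscanned subject can be evaluable. The Efficacy Evaluable rule asks for a tumor assessment, not a scan, and Section 11.3.1 provides caliper measurement of visible lesions. The conflict in the evaluability rule is therefore confined to subjects with no completed cycle or no assessment of any kind.

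**Conclusion.** The rule is wrong as written, and the point is minor. OS is the clearest part: it is measured from start of treatment in a set that requires survival to qualification, with no alternative set, although survival is collected on everyone who received a dose (Table 6, long-term follow-up note). For ORR, upward bias is probable but not certain. The illustrated 2 to 5 points sit inside an interval about 38 points wide, and the planned sensitivity analysis recovers part of them.

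Every size here depends on assumed losses, responder counts and OS medians. The OS shifts are scenarios. A reader might take the week-9 figure as a ceiling, but the scan window runs to day 70, and the model leaves out subjects who stop in Cycle 1 alive. In the other direction, early or discontinuation scans keep some subjects in who later die before week 9. Nor do the documents show that any reported result is affected, since no efficacy table is now planned.

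**What to change.** In the synopsis and Sections 12.1.2.3 and 12.1.6, make all treated subjects (the Safety Analysis Set, already defined) primary for ORR, PFS and OS. Count subjects with no post-baseline assessment as non-responders, and deaths before the first assessment as PFS events. Keep the Efficacy Evaluable and Efficacy Eligible Sets as supportive, and state this order in 12.1.6 in place of the open wording.

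In the sample-size rationale (synopsis and Section 12.1.1), remove the Efficacy Evaluable precondition for early progression and early death, and count both as non-responders.

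If any ORR is quoted after the early stop, give n/N of all treated with an exact 95% interval. State separately how many subjects lack a week-9 or confirmatory scan because the study was discontinued, since counting them as non-responders lowers confirmed ORR for a reason unrelated to the drugs.

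The cost is wording only: no new data and no new population. The downside is an ORR point estimate that is probably slightly lower.

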CLIA	Clinical Laboratory Improvement Amendment
C _{max}	Maximum concentration
CNS	Central nervous system
CPI	Checkpoint inhibitor
CR	Complete response
CRA	Clinical research associate
CrCl	Creatinine clearance
CRF	Case report form
CRO	Contract research organization
CT	Computed tomography
CTCAE	Common Terminology Criteria for Adverse Events
CTLA-4	Cytotoxic T lymphocyte-associated antigen 4
CV	Curriculum vitae
DLT	Dose-limiting toxicity
DM	Diabetes mellitus
DOR	Duration of response
ECG	Electrocardiogram
ECI	Events of clinical interest
ECOG	Eastern Cooperative Oncology Group
eCRF	Electronic case report form
EU	European Union

FAS	Full Analysis Set
FDA	Food and Drug Administration
GCP	Good Clinical Practice
GFR	Glomerular filtration rate
GI	Gastrointestinal
HBV	Hepatitis B virus
HCV	Hepatitis C virus
ICF	Informed consent form
ICH	International Conference on Harmonisation of Technical Requirements for Registration of Pharmaceuticals for Human Use
iCPD	Confirmed radiographic progression
iCR	Immune-based complete response
IEC	Independent Ethics Committee
INR	International normalized ratio
iPR	Immune-based partial response
irAE	Immune-related adverse event
IRB	Institutional Review Board
iRECIST	Modified RECIST for immunotherapies
iSD	Immune-based stable disease
ITT	Intent-to-treat data set
iUPD	Immune-based unconfirmed progressive disease
IV	Intravenous
K-M	Kaplan-Meier
LDH	Lactase dehydrogenase
mAb	Monoclonal antibody(ies)
MCH	Mean corpuscular hemoglobin
MCV	Mean corpuscular volume
MedDRA	Medical Dictionary for Regulatory Activities
mRECIST	Modified Response Evaluation Criteria In Solid Tumors
MRI	Magnetic resonance imaging
MTD	Maximum tolerated dose
NA	Not applicable
NCI	National Cancer Institute
NSAID	Nonsteroidal anti-inflammatory drug
NYHA	New York Heart Association
ORR	Objective response rate
OS	Overall survival
PD	Progressive disease; pharmacodynamics
PD-1	Programmed cell death protein 1
PFS	Progression-free survival
PG	Pharmacogenomics
PI	Principal investigator
PO	By mouth
PR	Partial response

PK	Pharmacokinetics
PS	Performance status
PT	Preferred term, prothrombin time
PTT	Partial thromboplastin time
Q2W	Every 2 weeks
Q3W	Every 3 weeks
QD	Once daily
RBC	Red blood cell
RECIST	Response Evaluation Criteria In Solid Tumors
RO	Receptor Occupancy
RP2D	Recommended Phase 2 dose
SAE	Serious adverse event
SAP	Statistical analysis plan
SD	Stable disease
SOC	System organ class
SOPs	Standard operating procedures
SUSAR	Suspected unexpected serious adverse reactions
T1DM	Type 1 diabetes mellitus
$t_{1/2}$	Terminal half-life
TEAEs	Treatment-emergent adverse events
T _{eff}	Effector T cell
TEMAV	Treatment-emergent markedly abnormal laboratory values
TME	Tumor microenvironment
T _{reg}	Regulatory T cell
TTR	Time to response
UA	Urinalysis
ULN	Upper limit of normal
US	United States
WBC	White blood cell
WHO DD	World Health Organization Drug Dictionary

4 **ETHICS**

4.1 Institutional Review Boards/Independent Ethics Committees

The protocol, informed consent form (ICF), and appropriate related documents must be reviewed and approved by an Institutional Review Board (IRB) or Independent Ethics Committee (IEC) constituted and functioning in accordance with International Conference on Harmonisation (ICH) E6 (Good Clinical Practice), Section 3, and any local regulations. Any protocol amendment or revision to the ICF will be resubmitted to the IRB/IEC for review and approval, except for changes involving only logistical or administrative aspects of the study (e.g., change in contract research associate(s) [CRAs], change of telephone number[s]). Documentation of IRB/IEC compliance with the ICH E6 and any local regulations regarding constitution and review conduct will be provided to the Sponsor.

A signed letter of study approval from the IRB/IEC chairman must be sent to the principal investigator (or if regionally required, the head of the medical institution) with a copy to the Sponsor before study start and the release of any study treatment to the site by the Sponsor or its designee (ICH E6, Section 4.4). If the IRB/IEC decides to suspend or terminate the study, the investigator (or if regionally required, the head of the medical institution) will immediately send the notice of study suspension or termination by the IRB/IEC to the Sponsor.

Study progress is to be reported to IRB/IECs annually (or as required) by the investigator or Sponsor, depending on local regulatory obligations. If the investigator is required to report to the IRB/IEC, he/she will forward a copy to the Sponsor at the time of each periodic report. The investigator(s) or the Sponsor will submit, depending on local regulations, periodic reports and inform the IRB/IEC (or if regionally required, the investigator and the relevant IRB via the head of the medical institution) of any reportable adverse events (AEs) per ICH guidelines and local IRB/IEC standards of practice. Upon completion of the study, the investigator will provide the IRB/IEC with a brief report of the outcome of the study, if required.

At the end of the study, the Sponsor should notify the IRB/IEC and Competent Authority within 90 days. The definition of the end of the study is the date of the data cutoff for the final analysis or last subject/last visit, including discontinuation from the study for any reason, whichever occurs later. The Sponsor should also provide the IRB/IEC with a summary of the study's outcome.

In the case of early termination/temporary halt of the study, the investigator should notify the IRB/IEC and Competent Authority within 15 calendar days, and a detailed written explanation of the reasons for the termination/halt should be given.

